#### **Core Population [CP]**

The core population is defined as all patients of the target population (TP) (definition see above), who are adequately treated according to the standard of care and within local label recommendations for their specific disease characteristics (cirrhotic status, genotype). The following patients will be excluded from the CP:

- · Patients with unknown fibrosis status
- · Cirrhotic patients with genotype 1a not receiving ribavirin
- Patients with genotype 1 for whom 2DAA instead of 3DAA is prescribed
- Patients with genotype 4 not receiving RBV

#### **Non-Core Population [NCP]**

Patients in the TP who are not in the CP.

## Core Population with Sufficient Follow-up [CPSFU {12, 24}]

In addition, the core population with sufficient follow-up data regarding SVR12 or SVR24, respectively, is defined as all CP patients,

- who have evaluable HCV RNA data ≥70 days or >126 days, respectively, after the last actual dose of the ABBVIE REGIMEN
- or a HCV RNA value ≥50 IU/mL at the last measurement
- or had HCV RNA <50 IU/mL at the last measurement, but no HCV RNA measurement ≥70 days or >126 days, respectively, after the last actual dose of the ABBVIE REGIMEN due to reasons related to safety (e.g. dropped out due to adverse event) or virologic failure (e.g. virologic failure such as relapse is reported in the electronic case report form (eCRF) but date and value of the corresponding HCV RNA test is missing).

This means only patients who had virological response at their last on-treatment or post-treatment measurement, but had no HCV RNA measurements ≥70 days or >126 days, respectively, post-treatment for reasons not related to safety or effectiveness (e.g. lost-to-follow-up or patient not willing to perform an additional HCV RNA test ≥70 days or >126 days, respectively, post-treatment) will be excluded from this analysis.

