 - Percentage of missed RBV treatment days in relation to the target number of RBV treatment days
- Co-morbidities and concomitant medication
- Serious and non-serious adverse events and pregnancy occurrences

- Questionnaires on PROs: e.g. EuroQol 5 dimension 5 level (EQ-5D-5L) questionnaire and work productivity and activity impairment (WPAI) questionnaire prior to treatment initiation, at EoT as well as 12 and 24 weeks after EoT

Data Sources:

Source documents are defined as original documents. The investigator will document patient data in his/her own patient files which will serve as source data for the study.

Study Size:

In phase III studies investigating the interferon-free ABBVIE REGIMEN \pm RBV, SVR12 rates of at least 90% were observed, even in difficult-to-treat CHC patients (e.g. cirrhotic G1a treatment experienced patients).

It is expected that 400 patients treated with the ABBVIE REGIMEN \pm RBV can be included and that about 90 to 95% of the patients enrolled will be evaluable in the core population (see below the definition of the core population). With 360-380 evaluable patients the width of the 95% confidence interval (CI) will not be wider than 6.5%. If the SVR12 rate is at least 95%, then with 360-380 evaluable patients the 95% CI will have a width of less than 4.8%.

Data Analysis:

The core population (CP) is defined as all patients of the target population (TP) (definition see above), who have started the treatment combination recommended in the current local label for their disease characteristics. Patients not receiving the treatment recommended in the local label will be summarized in the non-core population (NCP). In addition, the core population with sufficient follow-up data (CPSFU) is defined as all CP patients, who have (i) evaluable HCV RNA data ≥ 70 days after the last actual dose of the ABBVIE REGIMEN or (ii) a HCV RNA value ≥ 50 IU/mL at the last measurement or (iii) had HCV RNA < 50 IU/mL at the last measurement, but no HCV RNA measurement ≥ 70 days after the last actual dose of the ABBVIE REGIMEN due to reasons related to safety (e.g. dropped out due to adverse event) or incomplete efficacy information (e.g. virologic failure such as relapse is reported in the electronic case report form (eCRF) but date and value of the corresponding HCV RNA test is missing). The safety population (SP) is defined as all patients who received at least one dose of the ABBVIE REGIMEN.

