9.7 Data Analysis

9.7.1 Analysis Population, Time Windows and Handling of Missing Data

The target population (TP) is defined as all patients who fulfill the criteria specified in Section 9.2.1. The core population (CP) is defined as all patients of the TP, who have started the treatment combination recommended in the current local label for their disease characteristics. Patients not receiving the treatment recommended in the local label will be summarized in the non-core population (NCP). In addition, the core population with sufficient follow-up data (CPSFU) is defined as all CP patients, who fulfil one of the following criteria:

- (1) evaluable HCV RNA data ≥ 70 days after the last actual dose of the ABBVIE REGIMEN (i.e. data within the SVR12 time window)
- (2) a HCV RNA value ≥ 50 IU/mL at the last measurement post-baseline (i.e. no virological response achieved at the last measurement on-treatment or post-treatment)
- (3) HCV RNA < 50 IU/mL at the last measurement post-baseline, but no HCV RNA measurement ≥ 70 days after the last actual dose of the ABBVIE REGIMEN due to reasons related to safety (e.g. dropped out due to AE) or incomplete efficacy information (e.g. virologic failure such as relapse is reported in the eCRF but date and value of the corresponding HCV RNA test

Confidential Information

is missing). This means only patients who had virological response at their last on-treatment or post-treatment measurement, but had no HCV RNA measurements ≥ 70 days post-treatment for reasons not related to safety or effectiveness (e.g. lost-to-follow-up or patient not willing to perform an additional HCV RNA test ≥ 70 days post-treatment) will be excluded from this analysis.

The Safety Population (SP) is defined as all patients who received at least one dose of the ABBVIE REGIMEN.

In accordance with the non-interventional nature of the study all HCV RNA measurements will be performed at the sole discretion of the physician and all HCV RNA measurements have to be entered into the eCRF. All recorded HCV RNA values will be assigned to appropriate time points (baseline, on-treatment visits, EoT visit, post-treatment visits). The time windows for the assignments will be specified in the statistical analysis plan (SAP).

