9.9 Limitations of the Research Methods

The limitations of observational studies, such as uncontrolled confounding by lack of randomization, and difficulties to clearly interpret treatment effects in the context of missing data are well known. Their validity can be increased by accurate outcome measurements, documentation of the most common confounders, sufficient length of follow-up and by activities to obtain complete recording of available data as well as by searches for missing key data.

The most important outcome measure in this study is HCV RNA. Missing or unrecorded follow-up HCV RNA data can in particular lead to an underestimation of the real SVR rate as compared to the SVR rate of interventional trials. Highly sensitive and quantitative diagnostic tests are required to measure HCV RNA levels in blood. In an observational study each center will be using its own test – either commercially available or so-called “home-brew” tests – which might change from one visit to the next within a patient data set. The challenge is to accurately and consistently document test properties such as the LLoD and the LLoQ to put the results into perspective of prior outcomes from randomized controlled trials with (usually) central laboratory assessments for all trial participants.

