## 4. STATISTICAL CONSIDERATIONS AND ANALYTICAL PLAN

# 4.1 Primary and Secondary Parameters

## 4.1.1 Primary Effectiveness Parameter

The percentage of patients achieving SVR12 (HCV RNA <50 IU/mL 12 weeks [i.e. 70 to 126 days] after the last actual dose of the ABBVIE REGIMEN).

Please note, in the study protocol no upper boundary for the time window was specified. The upper boundary of 126 days was introduced to achieve consistency with other studies investigating the ABBVIE REGIMEN  $\pm$  ribavirin (RBV) for the treatment of CHC. For the handling of missing values see section 4.2.3.

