**Table 2 - Data Documentation Schedule** 

Assessment/ Procedure		Treatment Period		Post-treatment (PT) Period			
(only available data to be collected; no diagnostic or monitoring procedures to be applied to the patients apart from those of routine clinical practice)	Baselin	On- treatment visits	Mid treatment visit for pts receiving 24 weeks of therapy	EoT b	Early PT visit	SVR 12 visit	SVR 24 visit
Patient authorization	X a						
Demographic information	Χ						
IL28B	Χ						
Relevant CHC disease characteristics	Х						
Liver fibrosis stage	Х						
CHC treatment history	Χ						
HCV genotype and subtype	Χ						
HCV RNA samples	Х	Х	Х	Х	Х	Χ	Χ
Clinical chemistry and hematology	Χ	Х	Χ	Х	Х	Х	Х
ABBVIE REGIMEN initiation documentation	Х						
ABBVIE REGIMEN adherence		Х	Χ	Х			
Concomitant medication	Χ	Х	Χ	Χ			
Relevant medical history, co-morbidities	Χ						
sAE, AE and pregnancy reporting	Х	Х	Х	Х	Xc	$X_q$	Xd
For patients receiving RBV: Evidence, in accordance with local label, that female patient or female partner of male patient is not pregnant	Х						
Patient questionnaires – WPAI, EQ5D-5L	Χ			Х		X	Х

Abbreviations: EoT = End of Treatment (at Week 12 or 24 or at premature discontinuation), PT = Post-Treatment

- a Written patient authorization must be obtained before any data documentation in the eCRF
- b Patients who prematurely discontinue should return to the site to document EoT data
- c Tolerability documentation until PT week 4
- d Pregnancy reporting for patients treated with DAA plus RBV

In accordance with the non-interventional nature of the study all HCV RNA measurements will be performed at the sole discretion of the physician and all HCV RNA measurements have to be entered into the eCRF. All recorded HCV RNA values will be assigned to appropriate time points (baseline, on-treatment visits, EoT visit, post-treatment visits) as follows:

Table 3 - Analysis Time Windows for HCV RNA

Phase	Time point	Time Window
Pre-Treatment	Baseline	Last value prior to start of study treatment (i.e.
		≤study day 1)
On-treatment		Study day during treatment period^#
		(Study day 1 = first treatment day)
Treatment Week	4 (RVR*)	15 - 42^
EoT	Actual EoT	Study day of last dose#
		(28 days prior to last dose - 7 days post last
		dose)
Post Treatment	12 weeks (SVR 12	>=70-126 days post last dose
	window)	
	24 weeks (SVR24	127-210 days post last dose
	window)	

^values must also be <= 7 days post last dose

#>=study day 2

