# 4.2.3 Handling of missing data

No data will be imputed for any effectiveness or safety analyses except for the analyses of the HCV RNA endpoints and certain PRO endpoints. The discussion of missing data imputation for the PRO endpoints is included in section 4.2.7.2.3.

HCV RNA values will be selected for an RVR, EOTR and SVR analysis based on visit windows as defined in Table 3. When there is no HCV RNA value in a visit window based on defined visit windows, the closest values before and after the window, regardless of the value chosen for the subsequent and preceding window, will be used for the flanking imputation described below. For analysis of RVR, EOT and SVR, if a subject has a missing HCV RNA value at a post-Day 1 visit but with undetectable or unquantifiable (≤50 IU/mL) HCV RNA levels at both the preceding value and succeeding value, the HCV RNA level will be considered undetectable or unquantifiable,

respectively, at this visit for this subject. In addition, if a subject has an unquantifiable HCV RNA level at the preceding value and an undetectable HCV RNA level at the succeeding value, or vice versa, the HCV RNA level will be imputed as unquantifiable at this visit for this subject.

For analyses of RVR, subjects still missing a value for the visit after flanking imputation will be imputed as a failure. For EoTR and SVR analysis, if there is no value in the appropriate window after flanking imputation but there is an HCV RNA value after the window, then it will be imputed into the EoTR or SVR window respectively. Subsequent to this flanking imputation, if a subject is missing a value for the visit window associated with the analysis, the subject will be imputed as a visit failure (i.e., not undetectable or unquantifiable).

If a subject starts another treatment for HCV, then all HCV RNA values for this subject measured on or after the start date of the new HCV treatment will be excluded from analyses. The subject will be considered a failure for summaries of viral response at all time points after the start of the new HCV treatment.

Due to the non-interventional nature of this study several different methods for determination of the HCV RNA value can be applied. For the purpose of the statistical analysis, a HCV RNA measurement is considered ≤50 IU/mL.

- if a PCR test was used

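### The SAP definition of the core population with sufficient follow-up omits the post-baseline limit of protocol 9.7.1, so a patient with only a viraemic baseline value can enter it as a failure

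*SAP*

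**What the plan says.** CPSFU is defined in three places.

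- Protocol 9.7.1 lists three alternative criteria. The second is "a HCV RNA value ≥ 50 IU/mL at the last measurement post-baseline", which the protocol explains in brackets as no response at the last on-treatment or post-treatment value. The third, for patients below 50 IU/mL with no late value for safety or effectiveness reasons, carries the same post-baseline limit.
- The protocol abstract gives a short form without the limit: "ii) a HCV RNA value ≥ 50 IU/mL at the last measurement or (iii".
- SAP 4.2.1 also has no limit: "or a HCV RNA value ≥50 IU/mL at the last measurement". Its third criterion likewise refers to the last measurement with no qualifier.

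Protocol 9.7.1 and SAP 4.2.1 both close with a sentence that begins "This means only patients who had virological response at their last on-treatment or post-treatment measurement". It says that these patients are the only ones excluded, provided they have no later value for reasons unrelated to safety or effectiveness.

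Two other SAP rules matter. SAP 4.2.2 treats baseline as one of the HCV RNA time points: "All recorded HCV RNA values will be assigned to appropriate time points (baseline, on-treatment visits, EoT visit, post-treatment visits) as follows". SAP 4.2.3 sets the default for an empty window: "if a subject is missing a value for the visit window associated with the analysis, the subject will be imputed as a visit failure".

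CPSFU is used for the sensitivity analysis of SVR12 (SAP 4.2.7.1) and as the population in which the SVR24 rate is reported (SAP 4.2.7.2.1). The primary SVR12 analysis uses CP.

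**The concern.** A set meant to contain patients with enough follow-up should not take in a patient with no follow-up HCV RNA at all and count that patient as a treatment failure. The literal SAP wording allows this.

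Protocol 9.9 names the risk: "Missing or unrecorded follow-up HCV RNA data can in particular lead to an underestimation of the real SVR rate". CPSFU is the analysis that sets aside patients with uninformative follow-up, so the wording works against its purpose. It also treats the same cause of loss in two ways. A patient lost for unrelated reasons after an on-treatment response is left out, while a patient lost for the same reasons before any on-treatment test is counted as a failure.

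Two programmers could therefore build different CPSFU sets from the same SAP and each defend the result.

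**Working it through.** **The plan's own figure.** The only planning figures are the Clopper-Pearson 95% interval widths in protocol 9.5 and SAP 3.2. Recomputed for n = 340, 360 and 380, they are 6.67, 6.47 and 6.29 points at 90%, and 4.95, 4.80 and 4.66 points at 95%. The plan states 6.7, 6.5 and 6.3, and 4.9, 4.8 and 4.7. These agree within rounding. The point does not depend on them, but they give a scale.

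**Applying the rules to one patient.** Take a CP patient with a baseline value of 50 IU/mL or more and no later HCV RNA value.

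| Text | Result |
|---|---|
| Protocol 9.7.1, criteria list | Meets none of the three criteria: not in CPSFU |
| Protocol 9.7.1, closing sentence | Has no on- or post-treatment response, so is not among those excluded |
| Protocol abstract, read literally | Meets criterion (ii): in CPSFU |
| SAP 4.2.1, criteria list, read literally | Meets criterion 2: in CPSFU |
| SAP 4.2.1, closing sentence | Not among those excluded |
| SAP 4.2.3 | No flanking or later value to impute from: failure |

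The result in each row is the same whatever the reason for the missing follow-up. Patients with a post-baseline value of 50 IU/mL or more who are then lost meet criterion 2 under every text, so they are unaffected. The omission in criterion 3 matters little, because it would need a baseline value below 50 IU/mL with nothing after it.

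**Size.** Let n be the other CPSFU patients, x the responders among them, and k the number of baseline-only patients. Leaving the k patients out gives x/n; counting them as failures gives x/(n + k). The drop is (x/n) × k/(n + k).

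Assumptions: k = 0 to 8, since the documents give no count. For SVR12, n = 360 to 380, which is the plan's expected evaluable number in CP, borrowed here for CPSFU. For SVR24, n = 300 to 340. Response among the others is 95%, with one row at 90%.

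| Rate | x/n | k = 0 | k = 1 | k = 4 | k = 8 |
|---|---|---|---|---|---|
| SVR12 | 342/360 | 95.00% | 94.74% | 93.96% | 92.93% |
| SVR12 | 361/380 | 95.00% | 94.75% | 94.01% | 93.04% |
| SVR12 | 324/360 | 90.00% | 89.75% | 89.01% | 88.04% |
| SVR24 | 323/340 | 95.00% | 94.72% | 93.90% | 92.82% |
| SVR24 | 285/300 | 95.00% | 94.68% | 93.75% | 92.53% |

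For example, at n = 360 and k = 1 the drop is 0.95 × 1/361 = 0.26 points. Across the rows, one patient costs 0.25 to 0.32 points. At n = 360 and k = 4 the Wilson 95% interval moves from 92.2–96.8% to 91.0–96.0%.

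Rates are also reported by genotype and cirrhosis status. In a stratum of assumed size 40, one such patient changes 37/39 = 94.9% to 37/40 = 92.5%, a drop of 2.4 points. In one of 20, 18/19 = 94.7% becomes 18/20 = 90.0%, a drop of 4.7 points.

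**The case against.** **The SAP's context favours the post-baseline reading.** The set is named for its follow-up data, a pre-treatment value is not follow-up, and the closing sentence speaks of on- and post-treatment values. A careful programmer could arrive at the 9.7.1 list. This stands, and it is a main reason why the point is minor. It does not remove the gap, because the criterion itself does not say so and the closing sentence does not exclude the patient.

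**A reader might infer that the SAP changed the protocol without saying so.** The documents do not support that. The SAP wording agrees with the protocol's own abstract, so the inconsistency already exists within the protocol. The SAP does announce its new upper limit on the SVR12 window ("Please note, in the study protocol no upper boundary for the time window was specified") and its replacement of the laboratory shift tables. It does not announce the move from Clopper-Pearson to Wilson intervals, or from SVR12 to SVR24 as the regression outcome. The absence of a note here therefore says little about intent.

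**A reader might infer that the protocol clearly excludes every patient without a post-baseline value, so that all should be dropped.** The 9.7.1 list points that way, but its closing sentence does not. Criterion 3 also keeps patients without late data when the reason is safety or reported virologic failure. A blanket exclusion would remove, for example, a patient who stopped for an adverse event before any on-treatment test, and so would raise the CPSFU rate.

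**Such patients may be rare or absent.** This stands. HCV RNA is scheduled at several visits after baseline, and patients who stop early are asked to return for end-of-treatment data. On the other hand, testing is at the physician's discretion, and values are recorded only where routine practice provides them. Disposition tables and listings would also make much of any effect visible.

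**Conclusion.** The inconsistency is real and its severity is minor. The SAP criterion, taken literally, admits a baseline-only viraemic patient as a failure; the protocol 9.7.1 list does not admit that patient; and the closing sentence in both documents leaves the case open.

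The effect is confined to the CPSFU sensitivity analysis of SVR12 and the CPSFU SVR24 rate. It is about 0.25 to 0.3 points per patient overall, against a planned interval width of 4.7 to 6.5 points for 360 to 380 patients, and more in small strata. The per-patient figure depends little on the assumed n and response rate. Totals for more than one patient, and the stratum examples, rest wholly on assumed counts, and the true count may be zero.

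A reader might take this as a bias in the primary result. It is not: the patient is a failure in the CP analysis whichever CPSFU rule is used, so the primary SVR12 estimate does not move.

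**What to change.** In SAP 4.2.1, add the post-baseline limit to criteria 2 and 3, as in the protocol 9.7.1 list. That alone leaves the closing sentence in conflict with the list, so also state how CP patients with no post-baseline HCV RNA value are handled, and reword the sentence so that it no longer claims to name the only exclusions.

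The statement should carry over the reason test of criterion 3. Patients with no post-baseline value for reasons unrelated to safety or effectiveness are excluded from CPSFU. Those lost for safety reasons, or with reported virologic failure, stay in as non-responders. If the sponsor prefers another rule, it should be stated before the analysis.

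Report the number of CP patients with no post-baseline value, with reasons, in the disposition table already planned under SAP 4.2.5. Align the protocol abstract and the 9.7.1 closing sentence at the next amendment.

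The cost is a few words in the SAP and one row in a planned table, with no new data. The downside is a slightly smaller CPSFU denominator if any such patients exist; they remain failures in the primary CP analysis.

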#### Safety population [SP]

The safety population is defined as all enrolled patients who received at least one dose of the ABBVIE REGIMEN. The prescribed ABBVIE REGIMEN needs to be known.

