9.7.6 Tolerability Analysis

All tolerability variables will be summarized using descriptive statistical methods for the SP stratified by type of combination treatment and scheduled treatment duration.

All SAEs, non-serious AEs and pregnancy occurrences are to be reported for patients included in the study (see Section 11.0 and 9.2.3). AEs will be coded using MedDRA. The number and percentage of patients with treatment-emergent AEs (i.e. any reported event that begins or worsens in severity after initiation of study drug through 30 days post-study drug dosing) will be tabulated by primary MedDRA SOC and PT. Corresponding summary tables will be provided for all serious treatment-emergent AEs. The tabulation of the number of patients with treatment-emergent AEs by severity and relationship to study drug will also be provided. Patients reporting more than one AE for a given MedDRA PT will be counted only once for that term using the most severe incident for the severity summary table and the most related for the relationship summary table. Patients reporting more than one type of event within a SOC will be counted only once for that SOC.

Additional details of the analysis of AEs will be specified in the SAP.

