#### **Target Population [TP]**

Patients will be included if the following applies:

- Age at least 18 years
- Confirmed CHC with genotype 1 and/or 4 only, receiving combination therapy with the interferon-free ABBVIE REGIMEN ± RBV. The prescribed ABBVIE REGIMEN needs to be known.
- Have voluntarily signed and dated a patient authorization to use prior to inclusion into the study
- Must not be participating or intending to participate in a concurrent interventional therapeutic trial

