## 4.2.8 Analyses of Safety

All safety variables will be summarized for patients in the SP using descriptive statistical methods stratified by treatment regimen and cirrhosis status and overall.

An overview of tables for the individual values is given in Table 12.

The layouts of the tables mentioned above are provided in Part II of the SAP (Table Shells).

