#### 4.2.8.3 Adverse Events

All tolerability variables will be summarized using descriptive statistical methods for the SP stratified by treatment regimen and cirrhosis status and overall.

AEs will be coded using MedDRA. A glossary will show the verbatim terms and the corresponding coded terms used (see Table 12).

The number and percentage of patients with treatment-emergent AEs (i.e. any reported event that begins or worsens in severity after initiation of study drug through 30 days post-study drug dosing including those who are related to the study drug independent of the occurrence and those where the date of onset is missing) will be tabulated by primary MedDRA SOC and PT.

Corresponding summary tables will be provided for all serious treatment-emergent AEs and additional for all non-serious treatment-emergent AEs. In the table of non-serious AEs (that must exclude any SAE) only preferred terms that occurred at a frequency of >=5% in any treatment group will be displayed (no SOCs will be displayed).

The tabulation of the number of patients with treatment-emergent AEs by severity (AEs by severity [mild, moderate, severe], AEs leading to death, AEs leading to hospitalization) and relationship to study drug will also be provided (ABBVIE Regimen, ribavirin, medication error – paritaprevir/r-ombitasvir, medication error – dasabuvir, ABBVIE Regimen withdrawn, ribavirin withdrawn).

Patients reporting more than one AE for a given MedDRA PT will be counted only once for that term using the most severe incident for the severity summary table and the most related for the relationship summary table. Patients reporting more than one type of event within a SOC will be counted only once for that SOC.

The frequency of pregnancies will be displayed as well.

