Treatment-emergent AEs Leading to Withdrawal of ABBVIE Regimen by Treatment Regimen and Cirrhosis Status - SP - <country></country>	taewa_ <c>_tc_sp</c>	Safety population
Treatment-emergent AEs Leading to Withdrawal of Ribavirin in Patients taking RBV by Treatment Regimen and Cirrhosis Status - SP - <country></country>	taewr_ <c>_tc_sp_RB V</c>	Safety population: patients taking RBV
Listing of SAEs - SP - <country></country>	lsae_ <c>_sp</c>	Safety population
Glossary for AEs - <country></country>	tgae_ <c></c>	-
Co-medication by Treatment Regimen and Cirrhosis Status - SP - <country></country>	tcom_ <c>_tc_sp</c>	Safety population
Co-medication by Profile and by Treatment Regimen and Cirrhosis Status - SP - <country></country>	tcomp_ <c>_tc_sp</c>	Safety population
Associated Treated Condition by Treatment Regimen and Cirrhosis Status - SP - <country></country>	tatc_ <c>_tc_sp</c>	Safety population
Associated Treatment Profiles by Medication of Special Interest and by Treatment Regimen and Cirrhosis Status - SP - <country></country>	tatp_ <c>_mtc_sp</c>	Safety population

Glossary for Co-medication - <country></country>	tgcom_ <c></c>	-	
Laboratory Hematology by Treatment Regimen and Cirrhosis Status - SP - <country></country>	tlh_ <c>_tc_sp</c>	Safety population	
Laboratory Clinical Chemistry by Treatment Regimen and Cirrhosis Status - SP - <country></country>	tlc_ <c>_tc_sp</c>	Safety population	
CD4 and HIV RNA in Patients With HIV by Treatment Regimen and Cirrhosis Status - SP - <country></country>	tlch_ <c>_tc_sp_hiv</c>	Safety population	
Potentially Clinically Significant Laboratory Values by Treatment Regimen and Cirrhosis Status - SP - <country></country>	tpcs_ <c>_tc_sp</c>	Safety population	
Worst Laboratory Values by Treatment Regimen and Cirrhosis Status - SP - <country></country>	twlv_ <c>_tc_sp</c>	Safety population	

The layouts of the tables mentioned above are provided in Part II of the SAP (Table Shells).

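### The SAP's safety population adds a condition the protocol lacks (prescribed regimen known), so a dosed patient who fails it would be left out of every safety table and the SAE listing

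*SAP*

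**What the plan says.** The protocol defines the safety population twice, with one criterion each time. Section 9.7.1 has "The Safety Population (SP) is defined as all patients who received at least one dose of the ABBVIE REGIMEN", and the Abstract (Section 4.0) has "The safety population (SP) is defined as all patients who received at least one dose of the ABBVIE REGIMEN". On scope, Section 9.7.6 adds: "All SAEs, non-serious AEs and pregnancy occurrences are to be reported for patients included in the study".

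The SAP (Section 4.2.1, Safety population) keeps the one-dose criterion and attaches a second one: "received at least one dose of the ABBVIE REGIMEN. The prescribed ABBVIE REGIMEN needs to be known". The Target Population definition in the same section carries the same sentence: "The prescribed ABBVIE REGIMEN needs to be known".

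The SAP then ties its safety reporting to this population. Section 4.2.8 states: "All safety variables will be summarized for patients in the SP using descriptive statistical methods". Section 4.2.8.3 states: "All tolerability variables will be summarized using descriptive statistical methods for the SP". Section 4.2.8.4 does the same for laboratory data. In Table 12 the serious-event listing is titled "Listing of SAEs - SP".

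**The concern.** A safety population normally rests on exposure alone, so that no missing item other than dosing itself can remove a patient's events from the report. Here a gap in one baseline item, the prescribed regimen, would take out the patient and all of that patient's events. Describing tolerability is a stated secondary objective in both documents.

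The SAP identifies other departures from the protocol, namely the upper bound of the SVR12 window (Section 4.1.1) and the replacement of the laboratory shift tables (Section 4.2.8.4). It says nothing about this one. A reader who relies on the protocol would take the safety tables to cover every dosed patient.

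At stake is mainly the completeness of the SAE listing and the Total rows. The effect on percentages is secondary.

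**Working it through.** No figure in the plan is in dispute, so the check is first a comparison of texts and then an illustration of size.

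**1. The two definitions.**

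| Source | At least one dose | Prescribed regimen known |
|---|---|---|
| Protocol, Section 4.0 | required | not mentioned |
| Protocol, Section 9.7.1 | required | not mentioned |
| SAP, Section 4.2.1 | required | required |

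The SAP population is therefore a subset of the protocol's. The two coincide only if every dosed patient has a known prescribed regimen.

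**2. Does another output recover the patient?**

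- Table 12: every safety table and the SAE listing is assigned to the safety population or a subset of it. Only the two coding glossaries carry no population label, and they are not safety analyses.
- Target population: same condition, so the patient is out.
- Core population: a subset of the target population, so out. Non-core population: target minus core, so also out.
- Premature-termination tables (Table 6), in which death is a possible reason for not completing the study: planned for the core and safety populations only.
- What is left: the disposition table and listing for enrolled patients (Section 4.2.5) and the summary of exclusions with reasons (Section 4.2.10). The text assigns no AE or laboratory results to these outputs.

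**3. Is the condition needed?** A known regimen is needed to place a patient in a regimen row. It is not needed for a Total row or for a patient-level listing. The SAP's own groups already allow for unknowns: an unknown-fibrosis block in the safety groups and, for enrolled patients, an other/unknown genotype row. Section 4.2.8.3 also counts AEs with a missing onset date as treatment-emergent, so in that case a documentation gap does not lose an event.

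**4. Size, under assumptions.** The only documented input is the planned enrolment of 400 (Protocol Section 9.5), all taken here as dosed. The number excluded, k, and the SAE rate, r, are assumed. If exclusion is unrelated to having an SAE, the chance that at least one SAE patient is lost is 1 − (1 − r)^k:

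| k | r = 1% | r = 2% | r = 5% |
|---|---|---|---|
| 0 | 0% | 0% | 0% |
| 1 | 1.0% | 2.0% | 5.0% |
| 4 | 3.9% | 7.8% | 18.5% |
| 8 | 7.7% | 14.9% | 33.7% |

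For example, 1 − 0.95^4 = 18.5%.

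For the reported rate, assume 8 SAE patients in truth, 8/400 = 2.00%:

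- k = 1: 8/399 = 2.01% if the excluded patient had no SAE, 7/399 = 1.75% if that patient did.
- k = 4: 8/396 = 2.02% if none of the four had an SAE, 4/396 = 1.01% if all four did.

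The lower ends are arithmetical limits, not expectations. With no association, the expected number of SAE patients lost at k = 4 is 4 × 8/400 = 0.08.

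**The case against.** **The SAP may refine populations.** The protocol leaves further details of the analysis populations to the SAP (Sections 4.0 and 9.7.2) and requires tolerability to be stratified by combination treatment and scheduled duration (Section 9.7.6). A patient with unknown regimen cannot be placed in those strata. That explains why someone added the sentence. It does not justify removing the patient from the Total rows and the SAE listing. Narrowing an explicit all-dosed definition is a change rather than a detail.

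**The group may be empty.** This stands. Prescription precedes the offer to participate (Protocol Section 9.1). The regimen belongs to the inclusion documentation (Section 9.4.1.1) and is scheduled at baseline in Table 2, and eCRF checks and queries apply (Section 9.6.1). What remains is chiefly a patient known to be dosed but whose prescription, with or without dasabuvir, stays unknown after querying.

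**The exclusions are visible.** This also stands. Sections 4.2.5 and 4.2.10 of the SAP show who was excluded and why, so a reader would know that patients had left the safety population. The reader would not see their events.

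**A stronger reading to resist.** A reader might infer that the rule makes the regimen look better tolerated, because patients who stop or are lost early would have incomplete records. The documents do not support this. The condition concerns the prescribed regimen, recorded at baseline before on-treatment events, so early stopping does not by itself leave it unknown. A reader might also infer that SAEs would go unreported to the sponsor. They would not: Protocol Sections 11.1.4 and 11.1.5 set that duty without reference to the safety population.

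**Unseen shells.** Part II of the SAP (Table Shells) is not among the documents, so any handling of unknown regimen there cannot be checked.

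**Conclusion.** The point holds as a defect of definition. The SAP narrows the protocol's safety population without saying so, and no other planned output shows the AEs or laboratory safety results of a dosed patient who fails the added condition.

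The practical size is not stated, is probably very small and may be zero. The illustrative figures rest on an assumed number of exclusions and an assumed SAE rate, with 400 dosed. They show that overall rates would move little unless events happened to be concentrated among the excluded. The more consequential possibility is a single SAE patient missing from the listing. The documents support no direction of bias. The case for changing the text is that the condition contradicts the protocol, is unnecessary for the outputs that matter most, and is cheap to remove.

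**What to change.** Delete the sentence requiring a known prescribed regimen from the safety population definition in SAP Section 4.2.1, so that the definition matches Protocol Section 9.7.1. State that any dosed patient with an unknown regimen is counted in the safety population's Total rows and included in the SAE listing. If such patients exist, and only then, add a footnote or an unknown-regimen row to explain why the regimen rows do not sum to the total.

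The cost is one sentence removed and a minor table-shell change. It needs no new data. If an unknown-regimen row is used, it touches the by-regimen safety-population outputs in Tables 6, 7, 8 and 12; a footnote avoids most of that. If there are no such patients, no result changes.
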